*Blood transfusion (Korean Procedure Codes: X1001, X1002, X2011, X2012, X2021, X2022, X2031, X2032, X2041, X2042, X2051, X2052, X2061, X2062, X2071, X2072, X2081, X2082, X2091, X2092, X2101, X2102, X2111, X2112, X2121, X2122, X2131, X2132, X2141, X2142, X3010) will also be used to define other site bleeding history.

- Initial presentation of VTE
 - DVT (I80.2, I80.3)

- PE (I26.0, I26.9)
- Both DVT and PE
- Comorbidities (ICD-10 diagnostic code) will be measured within the 6-month period prior to the index date.
 - Antiphospholipid syndrome (D68.6, I82.9): As diagnosis of antiphospholipid syndrome is usually made after VTE diagnosis with subsequent diagnostic procedures, its presence will be evaluated within the 6-month period after the index date.
 - Asthma (J45)
 - Cancer (C00-C97): History of cancer (non-active) will be evaluated within a lifetime prior to the index date.
 - Chronic obstructive pulmonary disease (COPD; J40-J44)
 - Chronic kidney disease (N18, N19)
 - Chronic liver disease (B18, B19, K70-K77)
 - Diabetes mellitus (E10-E14)
 - Fracture (S22, S32, S42, S52, S62, S72, S82, S92, T10, T12)
 - Heart failure (I50)
 - Hyperlipidemia (E78)
 - Hypertension (I10-I15)
 - Ischemic heart disease (I24, I25)
 - Myocardial infarction (I21)
 - Stroke (I60-I64, I69, G45)
 - Trauma (T79, T98, V01–V99, W11–W17, W50–W52, W64, X34–X39, Y01–Y04, Y30–Y32)
- Previous use of medications (WHO-ATC code) will be measured within the 6-month period prior to the index date.
 - Corticosteroids (H02)
 - Nonsteroidal anti-inflammatory drugs (NSAIDs; M01A)
 - Angiotensin-converting enzyme (ACE) inhibitors (C09A, C09B)

- Angiotensin II receptor blockers (ARBs; C09C, C09D)
- Antiplatelet agents (aspirin [N02BA01], aspirin/dipyridamole [B01AC30], abciximab [B01AC13], beraprost [B01AC19], cilostazol [B01AC23], clopidogrel [B01AC04], iloprost [B01AC11], indobufen [B01AC10], limaprost [C04AX], ozagrel [R03DX], prasugrel [B01AC22], sarpogrelate [B01AC], ticagrelor [B01AC24], ticlopidine [B01AC05], tirofiban [B01AC17], treprostinal [B01AC21], triflusal [B01AC18])
- Azole antifungal agents (fluconazole [J02AC01], itraconazole [J02AC02], voriconazole [J02AC03], posaconazole [J02AC04])
- β -blockers (C07)
- Calcium-channel blockers (C08)
- Selective serotonin reuptake inhibitors (SSRIs; N06AB)
- Proton pump inhibitors (PPIs; A02BC)
- Diuretics (C03)
- Thiazides (C03A)
- Vasodilators (C01D, C04A)
- Estrogens (G03C)
- Cyclooxygenase (COX)-2 inhibitors (M01AH)

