- In the NOAC-based group, all analyses will be repeated stratified by each individual NOAC class (e.g, apixaban, dabigatran, rivaroxaban, edoxaban) to

PFIZER CONFIDENTIAL

identify the difference in baseline characteristics and treatment patterns between each NOAC class.

- To identify potential reasons for treatment change, clinical events preceding the first treatment change (major bleeding, thromboembolism diagnosis, complications of VTE, major surgery, active cancer, a new diagnosis of CKD or AKI, a new diagnosis of liver disease or abnormal liver function) will be measured within 30 days prior to the first date of treatment change. Patients can contribute with multiple events.
- All analyses of treatment patterns will be presented stratified according to the index anticoagulant treatment, and not overall or per drug class.

Phase II of the study (comparative)

Propensity score analysis

- To balance and adjust for any potential differences in baseline sociodemographic and clinical characteristics between treatment groups, propensity score (PS) methods will be implemented.
 - A logistic regression model will be used to estimate the predicted probability (propensity) of initiating each NOAC compared with warfarin given baseline covariates mentioned above. By using the estimated PS, we will apply the PS based on the inverse probability of treatment weights (IPTW), where the treatment group of interest will be given a weight of 1/PS, and the comparator group will be given a weight of 1/(1-PS) [4, 5]. The most extreme 1% of PS values (IPTW with trimming) will be excluded to improve comparability between exposure groups.

Main Analysis

- Sociodemographic and clinical characteristics will be summarized with means (STD) or median (IQR) for continuous variables and with count (proportions) for categorical variables for the two treatment comparisons of: apixaban vs warfarin, rivaroxaban vs warfarin, edoxaban vs warfarin and dabigatran vs warfarin (and NOAC vs NOAC, if scientifically feasible).
 - Differences in baseline covariates between users of different OACs will be assessed using the SD where the absolute SD <0.1 will be considered as well balanced.
- The incidence rate of major bleeding overall and by site will be presented as the total number of events per 1,000 person-years, with its 95% CIs estimated using the Poisson distribution.

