- The risk of major bleeding according to the treatment of interest will be investigated in time-to-event analyses using standard Kaplan-Meier methods.

- Cox proportional hazards model will be used to compare the safety outcome between users of different OACs, weighted on the estimated PS according to the IPTW approach.
 - Proportionality assumption will be tested by use of Schoenfeld residuals.

Subgroup Analysis

- The potential heterogeneity of treatment effects in selected subgroups of patients with VTE will be examined for the major bleeding as follows:
 - Aged <65 years vs. aged \geq 65 years
 - Females vs. males
 - Setting of VTE diagnosis (inpatient vs. outpatient)
 - Type of VTE (DVT without PE [ICD-10: I80.2, I80.3] vs. PE with or without DVT [I26.0, I26.9])
 - Major orthopedic surgery-provoked VTE
 - Major orthopedic surgery-provoked VTE is defined as an event preceded by knee arthroplasty, hip arthroplasty, or hip fracture surgery (National Procedure Codes: N0305, N0601, N0611, N0641, N0711, N2070, N0715, N2710, N0731, N0981, N0991, N1711, N3710, N1721, N3720, N1715, N4710, N1725, N4720, N2072, N2077, N2712, N2717, N3712, N3717, N3722, N3727, N4712, N4717, N4722 or N4727) within 3 months period prior to index date
 - With vs. without CKD stage 3 or 4 (N18.3, N18.4)
- P-for-interaction value <0.05 will be used to denote a significant difference between the two groups.

Sensitivity Analysis

- Vary the definition of treatment interruption/discontinuation to 15 and 60 days (allowing for varying non-adherence) to assess the effect this had on study outcomes.
- Four other approaches involving PS will be applied to determine the robustness of our study findings. First, we will vary the extreme value of PS in trimming process (most extreme 5%, and 10% will be excluded). Second, we will include the estimated PS, in addition to other covariates, into our multivariable Cox proportional hazards regression model. Third, we will stratify on the estimated PS in deciles. Last, we will apply another weighting approach, standardized mortality ratio weights, with the weights given as follows: 1 for the treatment group of interest and PS/(1 – PS) for the comparator group.[4]

- Exclude patients with a history of bleeding during the 6-month pre-index-date period in Phase II comparative analysis to evaluate the robustness of findings with respect to changes in underlying risk of patients

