Note: PAC, parenteral anticoagulants; IQR, Interquartile range; std, standard deviation

Table 13. Pre- and post-weighted baseline characteristics of patients with venous thromboembolism who newly initiated apixaban and warfarin.

Characteristics	Pre-weighted			Post-weighted		
	Apixaban		Warfarin-based therapy	Apixaban	Warfarin-based therapy	aSD
	N=	(%)	N=	(%)	N=	(%)
Follow-up (days; median, IQR)						
Age (years; mean±std)						
Age group (years; n, %)						
18-40						
40-65						
≥65						
Sex (n, %)						
Male						
Female						
Health insurance type (n, %)						
National health insurance						
Medical aid						
Index year (n, %)						
2012						
2013						
2014						
2015						
2016						
2017						
2018						
2019						
CCI score (mean±std)						
HAS-BLED score (mean±std)						
Comorbidities (n, %)						
Antiphospholipid syndrome						
Asthma						
History of cancer						
COPD						
Chronic kidney disease						
Chronic liver disease						
Diabetes mellitus						
Fracture						

Heart failure
Hyperlipidemia
Hypertension
Ischemic heart disease
Myocardial infarction
Stroke
Trauma
Previous use of
medications (n, %)
Corticosteroids
NSAIDs
ACE inhibitors
Angiotensin II receptor
blockers
Aspirin
 β -blockers
Calcium-channel
blockers
SSRI
Proton pump inhibitors
Diuretics
Thiazides
Vasodilators
Estrogens
Cyclooxygenase-2
inhibitors
Outpatient visits
(mean \pm std)

Note: ACE, angiotensin-converting enzyme; aSD, absolute standardized difference; CCI, Charlson comorbidity index; COPD, chronic obstructive pulmonary disease; IQR, interquartile range; NSAIDs, nonsteroidal anti-inflammatory drugs; PAC, parenteral anticoagulants; SSRI, selective serotonin reuptake inhibitors; std, standard deviation

Table 14. Pre- and post-weighted baseline characteristics of patients with venous thromboembolism who newly initiated rivaroxaban and warfarin.

Characteristics	Pre-weighted			Post-weighted		
	Rivaroxaban	Warfarin-based therapy	aSD	Rivaroxaban	Warfarin-based therapy	aSD
	N= (%)	N= (%)		N= (%)	N= (%)	
Follow-up (days; median, IQR)						
Age (years; mean±std)						
Age group (years; n, %)						
18-40						
40-65						
≥65						
Sex (n, %)						
Male						
Female						
Health insurance type (n, %)						
National health insurance						
Medical aid						
Index year (n, %)						
2012						
2013						
2014						
2015						
2016						
2017						
2018						
2019						
CCI score (mean±std)						
HAS-BLED score (mean±std)						
Comorbidities (n, %)						

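### Bleeding history has no propensity-score term or balance row of its own, so Tables 13–16 can meet SD <0.1 while it is unbalanced; the same shells also lag the SAP 8.4 covariate list

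*SAP*

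**What the plan says.** - **Propensity score.** SAP section 10 (Propensity score analysis) models the "predicted probability (propensity) of initiating each NOAC compared with warfarin given baseline covariates mentioned above". Section 10 lists no covariates, so the reference is to Potential Confounder(s) in SAP 8.4. Weights are 1/PS and 1/(1−PS). On trimming: "The most extreme 1% of PS values (IPTW with trimming) will be excluded".
- **Balance rule.** Under Main Analysis the rule is "Differences in baseline covariates between users of different OACs will be assessed using the SD where the absolute SD <0.1", and a covariate below that limit counts as well balanced. The only shells with standardized-difference columns are Tables 13–16, for example "Pre- and post-weighted baseline characteristics of patients with venous thromboembolism who newly initiated apixaban and warfarin".
- **Bleeding history.** It is not among the 15 comorbidities in SAP 8.4. It is one point of HAS-BLED, with all sites pooled. It does get a sensitivity analysis: "Exclude patients with a history of bleeding during the 6-month pre-index-date period in Phase II comparative analysis", with the stated aim of testing changes in patients' underlying risk.
- **Other covariates.** SAP 8.4 lists "Initial presentation of VTE" (DVT, PE, both), a class of 17 antiplatelet agents, and four azole antifungals.

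**The concern.** The outcome is major bleeding, and earlier bleeding bears directly on it; the plan's own sensitivity analysis treats it as altering underlying risk. A physician's choice between a NOAC and warfarin may depend on it. If the weights leave it unbalanced, the residual difference goes into the hazard ratio, and the SD <0.1 display would not reveal it, because the reader sees only a HAS-BLED mean to which bleeding contributes one point among several.

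The second matter is smaller. The tables meant to document balance after weighting do not show all the covariates that SAP 8.4 says are weighted on.

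**Working it through.** The plan gives no figure to reproduce; 0.1 is a decision limit. The check has four steps.

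**1. Rows against the covariate list**

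| Item | SAP 8.4 | Tables 1–4 (no SD columns) | Tables 13–16 |
|---|---|---|---|
| Bleeding history | inside HAS-BLED only as a named item | no row | no row |
| DVT/PE presentation | listed | row | no row |
| Antiplatelet agents | 17-agent class | row | 'Aspirin' only |
| Azoles | listed | row | no row |

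Tables 13–16 also carry an index-year row for 2012, although cohort entry starts on 1 Mar 2013. They look like shells that were not updated when 8.4 was.

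**2. Can the HAS-BLED total pin bleeding down?** It could if every other component were balanced separately under the same definition. From SAP 8.4:
- Hypertension has the same codes in both places (I10–I15).
- Renal, liver and stroke codes differ between HAS-BLED and the comorbidity list (renal: N18.3–N18.5, N19, Z94.0 and Z99.2 against N18 and N19).
- Alcoholism has no covariate of its own.
- Antiplatelets and NSAIDs share one point.

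So a balanced total can hide a bleeding difference offset by other components.

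**3. Dilution.** All inputs are assumed, since the documents give no bleeding prevalence and no HAS-BLED standard deviation.
- Standardized difference of bleeding = |p1−p0| / √{[p1(1−p1)+p0(1−p0)]/2}
- Contribution to the HAS-BLED row = |p1−p0| / s, with s = HAS-BLED standard deviation, taken as 1.0 to 1.5

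For 6% vs 10%: 0.04 / √[(0.0564+0.0900)/2] = 0.04/0.2706 = 0.148. Contribution: 0.04/1.5 = 0.027 to 0.04/1.0 = 0.040.

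| Prior bleeding | Own SD | Contribution to HAS-BLED row |
|---|---|---|
| 5% vs 8% | 0.122 | 0.020–0.030 |
| 6% vs 10% | 0.148 | 0.027–0.040 |
| 10% vs 15% | 0.152 | 0.033–0.050 |
| 10% vs 20% | 0.283 | 0.067–0.100 |

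In every case bleeding fails the limit on its own row, while its contribution to the HAS-BLED row stays below the limit or, at the extreme, reaches it.

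**4. Does weighting on HAS-BLED cure it?** Illustrative simulation: n = 49,224 (the apixaban–warfarin projection in SAP section 9), main-effects logistic score, inverse-probability weights, most extreme 1% trimmed, assumed prevalences and coefficients, HAS-BLED standard deviation 1.15. Eight Table 13 rows were simulated: age, HAS-BLED, hypertension, chronic kidney disease, chronic liver disease, stroke, NSAIDs and aspirin.

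| Run | Bleeding before weighting (NOAC vs warfarin; SD) | After weighting | Largest displayed row |
|---|---|---|---|
| Base | 7.2% vs 13.2%; 0.198 | 7.9% vs 12.0%; 0.137 | 0.050 |
| Variant | 7.2% vs 13.2%; 0.198 | 7.8% vs 12.2%; 0.150 | 0.051 |
| Bleeding drives drug choice more | 5.3% vs 14.7%; 0.320 | 6.0% vs 13.2%; 0.249 | 0.051 |

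HAS-BLED removed (0.198−0.137)/0.198 = 31% of the imbalance in the base run. In the base run DVT/PE ended at 0.001, azoles at 0.002 and non-aspirin antiplatelets at 0.071, because they or their class were in the score.

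Effect on the hazard ratio, with the base-run weighted prevalences and an assumed bleeding hazard h: [1+0.079(h−1)]/[1+0.120(h−1)]. For h = 2: 1.079/1.120 = 0.963. For h = 3: 1.158/1.240 = 0.934. This treats bleeding alone and ignores offsets from other HAS-BLED components.

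**The case against.** The best case for the plan has four parts.

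- **Bleeding history is not ignored.** It is a HAS-BLED component. Its intracranial codes also fall under the Stroke comorbidity (I60–I64, I69), which has its own balance row. Cerebrovascular (I60–I69), peptic ulcer (K25–K28) and I85.0 codes feed the CCI. A reader might infer that bleeding enters only through HAS-BLED; the code lists do not support that. The simulation results show no CCI row, so this overlap could make the real residual smaller. But most gastrointestinal codes outside these ranges, and the other-site codes and transfusions, have no second route as bleeding.
- **There are other checks.** The plan has wider trimming, PS plus covariates in the Cox model, deciles, SMR weights, and an E-value analysis (Protocol 9.9). So SD <0.1 is not the sole safeguard. The alternative PS analyses do, however, draw on the same covariate list. Excluding prior bleeders addresses the worry directly and is real mitigation, but it says nothing about balance in the main cohort.
- **Crude differences are visible.** Tables 1 and 3 give index VTE event and antiplatelets by drug, Table 19 gives numbers by VTE type, and Table 20 gives numbers after excluding prior bleeders. It would be wrong to say that no table shows them. None shows balance after weighting.
- **DVT/PE, antiplatelets and azoles are adjusted for.** A reader of Tables 13–16 might infer that they were left out of the score and bias the hazard ratio. SAP 8.4 lists them and section 10 refers back to that list, so this does not follow. If a programmer took the shells as the covariate list, DVT/PE would stay at 0.23–0.24 in the simulation with all shown rows under 0.1; that is a reason to align the shells, not evidence of missing adjustment.

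**Conclusion.** The point holds in two parts of different weight.

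**Bleeding history: a modest analysis gap.** It has neither its own score term nor a balance row. Under assumed inputs it can remain at a standardized difference of about 0.14–0.15 (0.25 with stronger selection) while the displayed rows are at most about 0.05. A simulation with different assumed inputs took it from about 0.195 to 0.12–0.17, the same conclusion. The illustrative effect on the hazard ratio is a factor of 0.93 to 0.96 if warfarin users bled more before index, and the inverse (1.04 to 1.07) if NOAC users did; the documents do not settle the direction. That is small against the planning range for apixaban (0.31–0.75) and less so against rivaroxaban (0.77–1.19), which spans 1. The demonstration is that the check can pass with bleeding unbalanced, not that it will.

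**DVT/PE, antiplatelets and azoles: a reporting gap.** Balance after weighting is unreported; adjustment is not missing.

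**What to change.** 1. In SAP 8.4, add bleeding history as its own covariate: the HAS-BLED bleeding codes, including the transfusion codes for other sites, in the existing 6-month window. Call it bleeding history, not major bleeding, because those codes carry no admission or imaging requirement. Keep HAS-BLED in the score.
2. Give it a standardized-difference row in Tables 13–16, for all four comparisons.
3. In the same tables add rows for DVT/PE/both, antiplatelet agents as a class (keeping aspirin if wanted) and azoles.
4. State in section 10 that SD <0.1 applies to every covariate in the score, and name SAP 8.4 as that list.
5. Use the same bleeding codes for the sensitivity analysis that excludes prior bleeders, for which section 10 gives none.

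The cost is one extra score term, a few table rows and a sentence or two of SAP text. The codes are already specified and the window is the one used for HAS-BLED, so no new data are needed. The change is best dated before any Phase II outcome results are seen.

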- The risk of major bleeding according to the treatment of interest will be investigated in time-to-event analyses using standard Kaplan-Meier methods.
- Cox proportional hazards model will be used to compare the safety outcome between users of different OACs, weighted on the estimated PS according to the IPTW approach.

PFIZER CONFIDENTIAL

- Proportionality assumption will be tested by use of Schoenfeld residuals.

Subgroup Analysis

- The potential heterogeneity of treatment effects in selected subgroups of patients with VTE will be examined for the major bleeding as follows:
 - Aged <65 years vs. aged \geq 65 years
 - Females vs. males
 - Setting of VTE diagnosis (inpatient vs. outpatient)
 - Type of VTE (DVT without PE vs. PE with or without DVT)
 - Major orthopedic surgery-provoked VTE
 - Major orthopedic surgery-provoked VTE is defined as an event preceded by knee arthroplasty, hip arthroplasty, or hip fracture surgery (National Procedure Codes: N0305, N0601, N0611, N0641, N0711, N2070, N0715, N2710, N0731, N0981, N0991, N1711, N3710, N1721, N3720, N1715, N4710, N1725, N4720, N2072, N2077, N2712, N2717, N3712, N3717, N3722, N3727, N4712, N4717, N4722 or N4727) within 3 months period prior to index date
 - With vs. without CKD stage 3 or 4 (N18.3, N18.4)
- P-for-interaction value <0.05 will be used to denote a significant difference between the two groups.

Sensitivity Analysis

- Vary the definition of treatment interruption/discontinuation to 15 and 60 days (allowing for varying non-adherence) to assess the effect this had on study outcomes.
- Four other approaches involving PS will be applied to determine the robustness of our study findings. First, we will vary the extreme value of PS in trimming process (most extreme 5%, and 10% will be excluded). Second, we will include the estimated PS, in addition to other covariates, into our multivariable Cox proportional hazards regression model. Third, we will stratify on the estimated PS in deciles. Lastly, we will apply another weighting approach, standardized mortality ratio weights, with the weights given as follows: 1 for the treatment group of interest and PS/(1 – PS) for the comparator group.[25]

- Exclude patients with a history of bleeding during the 6-month pre-index-date period in Phase II comparative analysis to evaluate the robustness of findings with respect to changes in underlying risk of patients

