Note: ACE, angiotensin-converting enzyme; aSD, absolute standardized difference; CCI, Charlson comorbidity index; COPD, chronic obstructive pulmonary disease; IQR, interquartile range; NSAIDs, nonsteroidal anti-inflammatory drugs; PAC, parenteral anticoagulants; SSRI, selective serotonin reuptake inhibitors; std, standard deviation

Table 16. Pre- and post-weighted baseline characteristics of patients with venous thromboembolism who newly initiated dabigatran and warfarin.

Characteristics	Pre-weighted			Post-weighted		
	Dabigatran N= (%)	Warfarin- based therapy N= (%)	aSD	Dabigatran N= (%)	Warfarin- based therapy N= (%)	aSD
Follow-up (days; median, IQR)						
Age (years; mean±std)						
Age group (years; n, %)						
18-40						
40-65						
≥65						
Sex (n, %)						
Male						
Female						
Health insurance type (n, %)						
National health insurance						
Medical aid						
Index year (n, %)						
2012						
2013						
2014						
2015						
2016						
2017						
2018						
2019						
CCI score (mean±std)						
HAS-BLED score (mean±std)						
Comorbidities (n, %)						
Antiphospholipid syndrome						
Asthma						
History of cancer						
COPD						
Chronic kidney disease						
Chronic liver disease						
Diabetes mellitus						

Fracture
Heart failure
Hyperlipidemia
Hypertension
Ischemic heart disease
Myocardial infarction
Stroke
Trauma
Previous use of
medications (n, %)
Corticosteroids
NSAIDs
ACE inhibitors
Angiotensin II
receptor blockers
Aspirin
β-blockers
Calcium-channel
blockers
SSRI
Proton pump
inhibitors
Diuretics
Thiazides
Vasodilators
Estrogens
Cyclooxygenase-2
inhibitors
Outpatient visits
(mean±std)

Note: ACE, angiotensin-converting enzyme; aSD, absolute standardized difference; CCI, Charlson comorbidity index; COPD, chronic obstructive pulmonary disease; IQR, interquartile range; NSAIDs, nonsteroidal anti-inflammatory drugs; PAC, parenteral anticoagulants; SSRI, selective serotonin reuptake inhibitors; std, standard deviation

Table 17. Risk of major bleeding events in patients with venous thromboembolism who newly initiated oral anticoagulants associated with NOAC use versus warfarin

	No of Patients	No of Events	Person-years	Incidence rate* (95% CI)	Crude HR (95% CI)	IPT-Weighted HR (95% CI)
Warfarin-based						Reference (1.00)
Apixaban						
Rivaroxaban						
Edoxaban						
Dabigatran						

Note: CI, confidence interval; HR, hazard ratio; IPT, inverse probability of treatment.

*Events per 1000 person years.

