13. LIST OF FIGURES

Figure 1. Kaplan-Meier plot showing time to anticoagulant therapy interruption in patients with venous thromboembolism according to presence of active cancer.	65
Figure 2. Kaplan-Meier plot showing time to anticoagulant therapy switching in patients with venous thromboembolism according to presence of active cancer.	66
Figure 3. Kaplan-Meier plot showing time to anticoagulant therapy discontinuation in patients with venous thromboembolism according to presence of active cancer.	67
Figure 4. Trends in newly prescribed anticoagulants in patients with venous thromboembolism between Mar 2013 and Jun 2019.....	68
Figure 5. Cumulative incidence curves for the risk of major bleeding events associated with NOAC use versus warfarin	69
Figure 6. Number of weighted events, incidence rate, and hazard ratio of major bleeding events associated with NOAC use versus warfarin.	70

[figure not shown]

Figure 1. Kaplan-Meier plot showing time to anticoagulant therapy interruption in patients with venous thromboembolism according to presence of active cancer.

[figure not shown]

Figure 2. Kaplan-Meier plot showing time to anticoagulant therapy switching in patients with venous thromboembolism according to presence of active cancer.

[figure not shown]

Figure 3. Kaplan-Meier plot showing time to anticoagulant therapy discontinuation in patients with venous thromboembolism according to presence of active cancer.

[figure not shown]

Figure 4. Trends in newly prescribed anticoagulants in patients with venous thromboembolism between Mar 2013 and Jun 2019.

[figure not shown]

Figure 5. Cumulative incidence curves for the risk of major bleeding events associated with NOAC use versus warfarin

PFIZER CONFIDENTIAL

[figure not shown]

Figure 6. Number of weighted events, incidence rate, and hazard ratio of major bleeding events associated with NOAC use versus warfarin.

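### Read literally, the Phase II bleeding curves are unweighted, so the one planned display of bleeding risk over time could disagree with the IPT-weighted hazard ratio.

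*SAP*

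**What the plan says.** SAP section 10 (Phase II) opens with the propensity score, whose purpose is given as: "To balance and adjust for any potential differences in baseline sociodemographic and clinical characteristics between treatment groups". A score is estimated for each NOAC against warfarin, the most extreme 1% of score values are excluded, and the rest are weighted by 1/PS or 1/(1-PS).

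Under Main Analysis, two consecutive bullets set the time-to-event methods:

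- Curves: "The risk of major bleeding according to the treatment of interest will be investigated in time-to-event analyses using standard Kaplan-Meier methods".
- Cox model: "weighted on the estimated PS according to the IPTW approach".

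Protocol section 9.7 has the same pair; bleeding risk there too "will be investigated in time-to-event analyses using standard Kaplan-Meier methods".

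SAP section 13 lists Figure 5 as "Cumulative incidence curves for the risk of major bleeding events associated with NOAC use versus warfarin" and Figure 6 as "Number of weighted events, incidence rate, and hazard ratio of major bleeding events associated with NOAC use versus warfarin". The images are not available to this review.

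In SAP section 12, Table 17 is titled "Risk of major bleeding events in patients with venous thromboembolism who newly initiated oral anticoagulants associated with NOAC use versus warfarin". Its columns are patients, events, person-years, incidence rate, crude HR and IPT-weighted HR. It has one warfarin-based row, followed by one row for each of the four NOACs. Tables 18-20 use the same single warfarin row within each block.

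**The concern.** The plan expects NOAC and warfarin starters to differ at baseline and adjusts the Cox model for this. Readers usually take absolute risk, and its course over time, from the curve. A crude curve titled as risk associated with NOAC use versus warfarin would show patient selection together with any drug effect, beside a hazard ratio from which the measured selection has been removed.

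Two features of the plan raise the stakes. SAP section 5 says that all NOACs became available as first-line treatment after a reimbursement change in May 2015. That date lies inside the March 2013 to June 2019 accrual window, so the groups probably differ at least by calendar time. In addition, proportional hazards will be tested with Schoenfeld residuals, but no action is stated if the assumption fails. The curves would then carry much of the interpretation.

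**Working it through.** No stated figure is at issue. The check compares the wording and then illustrates what an unweighted curve could show.

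**1. Where weighting is named**

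| Item | Weighting stated? |
|---|---|
| SAP Tables 13-16 (baseline) | Yes, pre- and post-weighted |
| SAP Tables 17-19 (HR) | Yes, IPT-weighted HR |
| SAP Table 20 (sensitivity) | Yes, in the block labels |
| SAP Figure 6 | Yes, weighted events |
| Cox model, SAP 10 and Protocol 9.7 | Yes, IPTW |
| Kaplan-Meier bullet, SAP 10 and Protocol 9.7 | No; the method is called *standard* |
| SAP Figure 5 title | No |

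A programmer who follows this text would draw crude curves.

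**2. Which displays show bleeding over time**

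SAP Figures 1-3 show time to interruption, switching and discontinuation. Figure 4 shows prescribing trends. Figure 6 names counts, rates and HRs. Only Figure 5 shows bleeding risk over time. Figures 1-3 are titled as Kaplan-Meier plots and Figure 5 as cumulative incidence curves, so title and method text also differ on the estimator.

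**3. How far a crude curve could depart from the weighted result**

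Inputs from SAP section 9, apixaban versus warfarin: overall bleeding probability 1.19%, apixaban share 39.3%, HR 0.75 (upper end of the stated range).

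Assumptions, not in the documents: one binary confounder with 40% prevalence, a bleeding HR of R = 1.5 to 3 for that confounder, and an odds ratio of 0.5 to about 3 for receiving apixaban when it is present.

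When risks are small, the crude risk ratio is approximately

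HR × [1 + (R-1)·pA] / [1 + (R-1)·pW],

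where pA and pW are the confounder's prevalence among apixaban and warfarin starters. Weighting sets both to 40%, which leaves the HR. The extremes occur at R = 3:

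- Odds ratio 0.5 gives pA = 0.302 and pW = 0.464 (check: 0.393 × 0.302 + 0.607 × 0.464 = 0.40). With true HR 1.0, the crude ratio is (1 + 2 × 0.302)/(1 + 2 × 0.464) = 1.604/1.928 = 0.83.
- Odds ratio about 3 gives pA = 0.560 and pW = 0.296 (check: 0.393 × 0.560 + 0.607 × 0.296 = 0.40). With true HR 1.0, the crude ratio is 2.120/1.592 = 1.33.

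Exact cumulative risks, with the baseline hazard set so that overall risk is 1.19%:

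| True HR | Odds ratio | Crude risk, apixaban vs warfarin | Crude ratio | Weighted risk | Weighted ratio |
|---|---|---|---|---|---|
| 1.00 | 0.5 | 1.06% vs 1.27% | 0.83 | 1.19% vs 1.19% | 1.00 |
| 1.00 | about 3 | 1.40% vs 1.05% | 1.33 | 1.19% vs 1.19% | 1.00 |
| 0.75 | 0.5 | 0.87% vs 1.40% | 0.63 | 0.98% vs 1.30% | 0.75 |
| 0.75 | about 3 | 1.19% vs 1.19% | 1.00 | 1.01% vs 1.34% | 0.75 |

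Ratios come from unrounded risks. In the last row the crude curves coincide although the true HR is 0.75.

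**4. The shared warfarin row**

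Four propensity models, each with its own 1% exclusion, give four trimmed warfarin groups. Tables 13-16 reflect this with a separate warfarin column per pair. Tables 17-20 have one warfarin row per block. That row can describe the untrimmed warfarin cohort behind the crude HRs, but not four differently trimmed samples. In Table 17 a labelled crude HR column stands beside the counts. Tables 19 and 20 have no crude HR column, and the differences between trimmed samples can grow under Table 20's 5% and 10% trimming.

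**The case against.** The strongest reply is that neither document uses the word *unweighted*. The propensity paragraph stands ahead of the whole Phase II analysis and could be meant to govern the curves as well. Figure 5's title is silent and its image is unavailable. A reader might infer that the plan has committed itself to a confounded figure. The documents do not establish that; they support only the literal reading of *standard*, set against weighting named in the next bullet and in neighbouring displays. If weighted curves were intended, the text still has to say so.

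A reader might also take raw counts beside a weighted HR in Table 17 as an error. That does not stand: raw counts belong with the crude HR, which has its own labelled column. What remains is narrower, namely that one warfarin row cannot describe four trimmed samples.

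Finally, the formal comparison is the weighted Cox HR, which is unaffected, and Figure 6 may give a weighted rate. Both points are fair and limit the consequence. Neither supplies an adjusted risk over time.

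**Conclusion.** The point holds on the literal text. Both documents specify standard Kaplan-Meier for bleeding and attach IPTW to the Cox model, so the only listed display of bleeding risk over time would be unadjusted. Disagreement with the weighted HR is possible, not certain.

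The ranges above (crude ratio 0.83 to 1.33 under a true null, and 0.63 to 1.00 under a true HR of 0.75) rest on an assumed confounder. They show that either direction is possible; they do not forecast a bias. A reader might infer that crude curves would necessarily flatter the NOACs, but the documents report no imbalance from which to predict a direction.

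The shared warfarin row is a separate, smaller defect that holds whatever was intended for Figure 5. Neither issue alters the primary hazard ratio.

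**What to change.** - In SAP section 10 and Protocol section 9.7, replace the standard Kaplan-Meier wording with IPTW-weighted curves that use the same trimmed sample and weights as the Cox model. Draw one NOAC-warfarin pair per panel, since each pair has its own weighted warfarin group.
- State the estimator so that the method text and the Figure 5 title agree: either one minus Kaplan-Meier or a competing-risk cumulative incidence. In-hospital death ends follow-up in Phase II, so the two are not the same quantity.
- Label any crude curves as crude.
- For the weighted results in Tables 17-20, give a warfarin row per comparison with that comparison's trimmed N and events, and its person-years (Tables 19 and 20 have no such column now). Keep the shared row only for the crude, untrimmed comparison.

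Weighted risk differences at 6 and 12 months would be an optional addition. The plan sets no such time points for bleeding, and the correction does not need them.

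The cost is an edit to both documents, revised shells, some extra programming and longer tables. No new data are needed and the HR does not change.
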